## **16.0 Withdrawal of Subjects**

- 16.1 As this study consists of a one-time intervention, we do not anticipate any circumstance in which a subject will be withdrawn without their consent.
- 16.2 Subjects may choose to discontinue study participation at any time, for any reason, specified or unspecified, and without prejudice. Subjects may be discontinued from the study for any of the following reasons:
  - At the subject's or their parent's/LAR's request
  - At the discretion of the site investigator as deemed appropriate for any reason

Procedures for orderly termination will include a discussion with the parents or LAR for the reasons behind early termination.

16.3 If a subject withdraws from the research study, data that has already been collected may still be used; however, no new information will be collected except information related to adverse events or other safety issues.

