## 17.0 Risks to Subjects

17.1 As part of SOC, all patients enrolling in this study will have at least one functioning intravenous catheter placed during the SOC blood draw, hence no new IV access will be required. We expect that there may be some mild discomfort related to the performance of the ultrasound study itself and will monitor for this. Other than the discomfort from the ultrasound probe, we do not expect any other ultrasound-related discomfort. Patients will be monitored by licensed personnel during the study interval. Per standard of care, patients will return to the ED while the results of their gray scale ultrasound and CT, if one was taken, are obtained. ED staff will continue to monitor patients for any adverse event.

Reported risks related to Lumason administration include:

Adverse Reaction	Number	(%)
Any Adverse Reaction	340	5
Headache	65	1
Nausea	37	0.5
Dysgeusia	29	0.4
Injection site pain	23	0.3
Feeling hot	18	0.3
Chest discomfort	17	0.2
Chest pain	12	0.2
Dizziness	11	0.2
Injection site warmth	11	0.2

Serious cardiopulmonary reactions, including fatalities, have occurred uncommonly in adults during or shortly following administration of ultrasound contrast agents, including Lumason. These reactions typically occurred within 30 minutes of administration. Hypersensitivity reactions such as skin erythema, rash, urticaria, flushing, throat tightness, dyspnea, or anaphylactic shock have uncommonly been observed following the injection of Lumason. The exclusion criteria eliminate any subjects with a known cardiac abnormality or a known sensitivity to sulfur hexafluoride, so we do not anticipate that these reactions will occur. Resuscitation personnel and equipment will be available during the study treatment and follow-up period.

17.2 This study poses a minor increase over minimal risk as Lumason will be used off-label, but the intervention presents an experience that is reasonably commensurate with those inherent to the subject's medical situation. The only risks attributable to the study are those

of the adverse reactions listed above, as these patients will have already had an IV placed, and would have ultrasound as part of their appendicitis workup. Furthermore, Lumason is currently FDA approved, and in use at CMH, for other abdominal CEUS applications such liver lesions and vesicoureteral reflux in pediatrics.

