## 21.0 Provisions to Monitor the Data to Ensure the Safety of Subjects

This study proposes a one-time intervention of CEUS. Subjects will be monitored in real time at the time of and following the CEUS. Data collected will be evaluated after the first 10 subjects are enrolled.

- All data collected on subjects who receive study drug will be analyzed for safety. The proportion of patients with specific adverse events will be reported as well as the worst grade observed across all adverse events. The maximum confidence interval width for these estimates is 16.8%. If the observed estimated adverse event proportion is 10%, the 95% confidence interval is (5.3,15.6%).
- Safety information will be collected at the time of study visit when the patient is monitored during contrast administration.
- Safety data collection will begin with the first participant. Participants will be monitored in real time.
- The PI or an assigned co-investigator will be responsible for monitoring the data.
- Cumulative data will be reviewed on a weekly basis beginning with the first study participant.
- All data collected on subjects who receive study drug will be analyzed for safety. The proportion of patients with specific adverse events will be reported as well as the worst grade observed across all adverse events. The maximum confidence interval width for these estimates is 16.8%. If the observed estimated adverse event proportion is 10%, the 95% confidence interval is (5.3,15.6%).
- Any adverse event resulting from the contrast agent requiring an ICU admission will trigger an immediate suspension of the research.

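### The one automatic suspension rule (section 21.0) is tied to ICU need, so it does not fire for a life-threatening contrast reaction that resolves without the ICU

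*Protocol*

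**What the plan says.** Protocol section 21.0 ends with the only automatic suspension rule in the document: "Any adverse event resulting from the contrast agent requiring an ICU admission will trigger an immediate suspension of the research". The same section provides for real-time monitoring of each subject and two kinds of data review: "Data collected will be evaluated after the first 10 subjects are enrolled", and "Cumulative data will be reviewed on a weekly basis beginning with the first study participant". Neither review carries a criterion for action. The principal investigator or a co-investigator does the monitoring.

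Section 17.1 describes the serious risks: "Serious cardiopulmonary reactions, including fatalities, have occurred uncommonly in adults during or shortly following administration of ultrasound contrast agents, including Lumason". It says that these typically arise within 30 minutes. On hypersensitivity it lists, among others, "throat tightness, dyspnea, or anaphylactic shock have uncommonly been observed following the injection of Lumason". It adds that "Resuscitation personnel and equipment will be available during the study treatment and follow-up period".

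Section 6.3 returns children to the ED or floor after the scan, where staff keep watching for adverse events. Section 23.1 says how an adverse event from the study procedure is handled: the principal investigator reviews it, the IRB is told, and institutional policy governs the rest.

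**The concern.** The risk section is written in terms of how serious a reaction is. The stopping rule is written in terms of where the child ends up being cared for. The two usually go together, but not always. A child could have anaphylactic shock, or need resuscitation, be treated promptly by the team on hand, recover, and never need the ICU. Under the rule as worded, that event does not suspend the study.

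The agent is used off-label in children aged 8 to 17, and enrolment has been extended to all hours and every day. The purpose of an automatic rule is to pause dosing before anyone has had time to deliberate. What is at stake is whether the next child is dosed before a life-threatening reaction has been reviewed. No estimate, test or sample size is affected.

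**Working it through.** The protocol attaches no figure to the suspension rule, so there is nothing to reproduce. The check is a comparison of the text.

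**Step 1. Apply the rule to the events that section 17.1 foresees.**

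| Contrast-related event | Does the 21.0 rule fire? | What the protocol then states |
|---|---|---|
| Any event requiring ICU admission | Yes | Immediate suspension |
| Anaphylactic shock, resolved without ICU need | No | Review, IRB report, institutional policy (23.1) |
| Cardiopulmonary reaction needing resuscitation, resolved without ICU need | No | Same |
| Death before transfer to the ICU | Not explicit, but the wording can be read to cover it | Suspension if so read; otherwise as in 23.1 |
| Mild reaction such as headache or nausea | No, and reasonably so | Same as 23.1 |

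The second and third rows are the gap.

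**Step 2. Is treatment outside the ICU foreseen?** Yes. The 30-minute window in 17.1 falls while the child is in radiology, the ED or on the floor (6.3), and 17.1 makes resuscitation available during treatment and follow-up. The plan does not say that every such child then goes to the ICU.

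**Step 3. Does another provision supply the hold?**
- Section 16.2 allows discontinuation "At the discretion of the site investigator as deemed appropriate for any reason", but it concerns individual subjects, not the study.
- The look after 10 subjects and the weekly review in 21.0 state no threshold and no action.
- Section 23.1 requires review and reporting but states no pause while these are under way.
- The exclusions in 11.0 remove children with a known cardiac abnormality, pulmonary hypertension or known sensitivity. They lower the risk but cannot remove a first, unknown sensitivity.

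**Step 4. Would the event be recorded in a usable form?** Section 21.0 plans to report the share of patients with each adverse event "as well as the worst grade observed across all adverse events". The data points in 6.4, however, list symptoms (headache, nausea, altered taste, injection site reaction, flushing, chest pain, dizziness) and a free comment field. They do not list a grade, anaphylaxis, resuscitation or ICU admission.

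**Step 5. Can the gap be sized?** Not from the documents. The table in 17.1 gives rates for common reactions (5% for any, 0.2% for chest pain) but none for anaphylactic shock or serious cardiopulmonary reactions. No share that would avoid the ICU is given either. The only related figure is the planned accrual in 10.0, converted to weeks: 15 × 12 / 52 = 3.5 and 20 × 12 / 52 = 4.6 children per week. That is the pace of dosing, not the size of the gap.

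**The case against.** The best case for the present rule is that ICU need is objective and clear, and that an automatic stop need not list every serious event when other oversight covers the rest. A shock or resuscitation would happen in front of staff and, under 23.1, would be reported to the IRB. The investigator and the IRB can stop dosing at any time. Many such reactions would need the ICU, and the cardiopulmonary reports in 17.1 are from adults. A severity criterion also brings judgment back in, since someone must decide that an event was life-threatening and due to the contrast.

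Most of this stands, and it is why the gap is narrow. It does not make the rule cover the two events in question. Reading the trigger as clinical need rather than actual admission does not help either, because a reaction that resolves without ICU need fails both readings.

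A reader might infer more than the text supports in four ways:
- **That a hold would rest purely on investigator or IRB discretion.** Section 23.1 refers to an institutional policy that is not shown and that may itself require a hold.
- **That 3.5 to 4.6 further children would be exposed.** This is only the accrual rate, and it would apply only if nobody acted for a week after a witnessed emergency.
- **That the study would carry on after a death.** A fatal reaction can reasonably be read as one that required ICU care.
- **That severity will in any case be on record.** The planned report of worst grade points that way, but 6.4 has no item for it.

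**Conclusion.** The point holds in a limited form. The only automatic suspension rule stated in the protocol does not fire for a contrast-related life-threatening reaction of a kind named in 17.1 that is treated and resolves without ICU need. For that case no hold is stated, only review, IRB reporting and an institutional policy whose content is unknown.

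No probability or harm rate can be given, because both the rate of such reactions and the share that would avoid the ICU would have to be assumed. The conclusion assumes only that such a reaction can sometimes resolve without the ICU, which the protocol neither states nor rules out. This is an imprecisely drawn rule, not an absence of oversight. Low-to-moderate priority, and worth correcting because the correction is so cheap.

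**What to change.** Amend the last bullet of section 21.0 so that dosing is suspended, pending review by the principal investigator and the IRB, after any contrast-related event that is fatal, is life-threatening (including anaphylactic shock or any reaction needing resuscitation), or requires ICU admission, wherever it is treated. Naming fatal events removes any doubt about a death before transfer.

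Add matching items to the data points in 6.4: anaphylaxis, resuscitation, ICU admission and a severity grade. The trigger can then be checked against the record.

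The cost is one sentence and a few form fields in an amendment, plus a rare, brief enrolment pause for an event that did not need the ICU. Naming anaphylactic shock and resuscitation keeps the remaining judgment small, although attribution to the contrast still has to be decided, as it does under the present rule.

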## **22.0 Provisions to Protect the Privacy Interests of Subjects**

- 22.1 Subject confidentiality and privacy will be maintained by recording only de-identified data onto the REDCap research record. A subject-specific ID will be assigned to each record. A linking master list will be created and kept in a separate REDCap data instrument.
- 22.2 During the informed consent process the purpose of the research study, study procedure, potential risks and societal benefits will be thoroughly explained to the subject and his/her parents or LAR. They will be given the opportunity to ask questions during the informed consent process and at any time during or after study participation.
- 22.3 The research team will access the patient's medical record in order to collect pertinent data points generated through clinical care. Only the minimum necessary data will be recorded in REDCap. The researchers alone will

have full access to the REDCap database. A subject-specific ID will be assigned to each record. A linking master list will be created and kept in a separate REDCap data instrument.

22.4 PHI to be accessed and/or recorded for this research study includes the following:

- names/initials- accessed
- dates- recorded
- medical record number-recorded
- hospital account number-recorded

22.5 HIPAA Authorization from subjects/parents to access and/or record PHI for this research study will be included within the permission/assent form(s).

## **23.0 Compensation for Research-Related Injury**

23.1 Regular clinical review will minimize the risk of complications or harm as a result of study participation. In the event that an adverse event results from the study procedure, it will be reviewed by the principal investigator, reported to the IRB, and dealt with per institutional policy. Treatment will be available at CMH and will be provided at the usual charge. Payment for this treatment will be the participant's responsibility as this research study does not have funds set aside to pay research participants if the research results in harm or complications. The approved IRB P/A will include known possible adverse events of study participation as well as payment responsibility for any adverse event.

23.2 N/A.

## **24.0 Economic Burden to Subjects**

24.1 There is no costs to patients for participating in this research study. Patients who agree to study participation will not be charged for the Lumason contrast agent nor for the CEUS. They will be charged for all standard of care procedures including the standard (non-contrast/gray scale) ultrasound, and any other diagnostic workup and treatment for appendicitis they would receive whether or not they were enrolled in the study.

## **25.0 Permission/Accent/Consent Process**

25.1 Permission/assent will be obtained on all subjects wishing to participate.

- The p/a process will take place in the ED at the patient's bedside.

- While eligible candidates will be given all necessary information to make an informed decision and will have every opportunity to ask questions, the waiting period available between informing the prospective subject and obtaining p/a will be limited as this study does not intend to delay standard of care treatment. A potential subject who has not affirmatively signed the p/a form prior to the standard gray scale ultrasound will continue through SOC treatment without prejudice.
- We will be following CMH research policies on informed consent.
- We will not be obtaining permission/assent via telephone as such is not feasible for this study.
- This pediatric research study will be conducted entirely in the state of Missouri and will involve enrolling minors under the age of 18.
- Parental permission will be obtained from one parent or LAR.
- Other than biological parents, LARs such as an adoptive parent will be allowed to consent for a child's participation in this study.
- Assent will be obtained from all children participating in this study unless the study team member attempting to obtain P/A determines the child is not capable of providing assent.
- The child's assent will be documented on the combined P/A form.
- In the event assent may not be obtained, the reason(s) will be documented in the provided section of the P/A form.

#### Consent at 18 years of age, when minor subjects become adults

We are requesting a Waiver of Consent at Age 18. Active participation of the subject will be concluded, as this is a single-visit ultrasound study. Data collection will be completed before the subject turns 18. Data analysis might continue after some subjects have turned 18, but this is explained in the Permission/Accent form they would have signed at the time of enrollment. Furthermore, re-consenting at age 18 would be impracticable for this study, as these subjects will be emergency appendicitis patients at CMH, and most will be unlikely to return for follow up appointments after reaching 18.

Waiver or Alteration of Parental Permission or Child Assent Process (permission and/or assent will not be obtained, required information will not be disclosed, or the research involves deception)

N/A

Waiver or Alteration of Consent Process (consent will not be obtained, required information will not be disclosed, or the research involves deception)

N/A

Non-English Speaking Subjects

N/A

Cognitively Impaired Adults

N/A

Adults Unable to Consent

N/A

## **26.0 Process to Document Permission/Accent/Consent**

26.1 Study staff will be following [CM Research Policy 10.04 Obtaining Permission/Accent/Consent.](#)

26.2 N/A

26.3 N/A

## **27.0 Setting**

27.1

- Study team members (specifically surgery fellows and attending's) will identify patients presenting to the CMH Adele Hall Emergency Department with concerns of appendicitis, and will approach patients/parents to recruit for the study.
- Ultrasounds will be performed in the Radiology department at CMH Adele Hall. Data will be collected by study team members at CMH Adele Hall Emergency, Radiology and Surgery departments.

## **28.0 Resources Available**

28.1 Resources available to conduct this research study include the following:

- The research team anticipates access to approximately 375 potential subjects as prior data reveals 375 children are diagnosed with appendicitis at our institution each year.

- This study will take place entirely within CMH Adele Hall campus, specifically in the Emergency, Radiology and Surgery departments.
- The study will involve approximately 60 minutes of patient interaction. Data collection and review of aggregate data will continue while the project is ongoing.
- While it is not anticipated that subjects will need additional medical or psychological services as a result of participating in this study, care will be available at CMH and will be provided at the usual charge should the need arise.
- All study team members will have read the protocol and any standard operating procedures for the study. All study team members will have completed their required research trainings to conduct research at CMH and be knowledgeable of their duties and functions as evidenced by their signature in the study delegation log.

## **29.0 Multi-Site Research**

N/A

